#### **6.1.2.11 Disease Assessment during Trial**

Disease assessments should be performed per the frequency defined in Section 5.0 – Trial Flow Charts. There is a  $\pm 3$  day window for assessments performed after Day 1. Disease assessments should not be delayed for delays in cycle starts.

Disease assessments should continue to be performed until documented disease progression, the start of new anti-cancer treatment, withdrawal of consent, death, or the end of the study, whichever occurs first. Disease assessments should be performed to confirm stringent CR or as clinically indicated.. Subjects who have unconfirmed disease progression may continue on treatment until progression is confirmed at the next scheduled assessment.

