#### **6.1.4.5.1 Survival Follow-up**

Once a subject experiences confirmed disease progression or starts a new anti-cancer therapy, the subject moves into the survival follow-up phase and should be contacted by telephone every 12 weeks to assess for survival status until death, withdrawal of consent, or the end of the study, whichever occurs first.

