##### **7.1.6.1 Efficacy Endpoints**

Key efficacy endpoints for the trial include the following as assessed by IMWG:

- PFS: defined as the time from Day 0 of ASCT to progressive disease (PD) or death, whichever occurs earlier, per IMWG criteria by investigator assessment. Subjects without documented PD/death will be censored at the last disease assessment date.
- Complete response, stringent complete response, and very good partial response rate (CR + sCR + VGPR) rate using IMWG criteria. Response rates will be determined with the following baselines 1) Prior to ASCT 2) Cycle 1 day 1 of study drug or screening visit, whichever is higher.
- ORR: Defined as the proportion of subjects who have achieved sCR, CR, VGPR or PR according to the IMWG criteria by investigator assessment. Subjects with missing outcome on objective response will be considered non-responders. Response rates will be determined with the following baselines 1) Prior to ASCT 2) Cycle 1 day 1 of study drug or screening visit, whichever is higher.
- DOR: defined as the time interval between the date of first response (sCR, CR, VGPR, PR) and the date of first documented disease progression.
- TTP: defined as the time from 1) Day 0 ASCT and 2) Date of enrollment to progressive disease (PD) per IMWG criteria by investigator assessment. Subjects without documented PD or death will be censored at the last disease assessment date, and subjects who died without documented PD will be censored at the time of death.

- OS: defined as the time from Day 0 ASCT to death from any cause.

In addition, overall survival (OS) and change from baseline in bone marrow/aspirate PD-L1 expression, T-cell subsets, and cytokine analysis will be evaluated.

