### **7.1.7 Analysis Populations**

#### **7.1.7.1 Efficacy Analysis Populations**

The Full Analysis Set (FAS) population will serve as the primary population for the analysis of response rate data in this study. The FAS population consists of all subjects who:

- receive at least one dose of study treatment
- have a post baseline disease assessment OR discontinue the trial due to progressive disease/drug-related AE

The Intent-to-Treat (ITT) population will serve as the primary population for the analyses of PFS, TTP and OS in this study. The ITT population consists of all enrolled subjects.

The analysis of response duration is based on all responders.

Details on the approach to handling missing data are provided in Section 7.1.8 Statistical Methods.

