## 7.1.8 Statistical Methods

### 7.1.8.1 Statistical Methods for Efficacy Analysis

Kaplan-Meier estimates and corresponding 95% confidence intervals of time to event endpoints, including PFS, OS, TTP and DOR, will be provided.

For key efficacy endpoints including CR + sCR + VGPR rate + ORR, the point estimate, 90% confidence interval and p-value for testing response rate is greater than the historical control for each arm will be provided using exact binomial distribution.

Table 13 Summarizes key efficacy analyses.

Table 13 Analysis Strategies for Key Efficacy Variables

Endpoint/Variable (Description, Time Point)	Primary vs. Supportive Approach	Analysis Population	Statistical Method	Missing Data Approach
Primary				
PFS	P	ITT	Summary statistics using Kaplan- Meier method	Censored at last disease assessment date
Secondary				
ORR per IMWG criteria based on investigator assessment	P S	FAS ITT	Exact test of binomial parameter	Subjects with missing data are considered as non-responders
CR+sCR+VGPR response rate per IMWG criteria based on investigator assessment	P S	FAS ITT	Exact test of binomial parameter	Subjects with missing data are considered as non-responders
OS	P	ITT	Summary statistics using Kaplan- Meier method	Censored at the last date known to be alive
TTP	P	ITT	Summary statistics using Kaplan- Meier method	Censored at the last non- PD assessment date
DOR	P	All responders	Summary statistics using Kaplan- Meier method	Non-responders are excluded in analysis

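### Time to progression (TTP) has two censoring rules for patients who die without documented progression; the rule in 7.1.6.1 counts unassessed time as progression-free only for those who later die

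*Combined protocol and SAP*

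**What the plan says.** TTP is a secondary objective (section 2.2, objective 4). Section 7.1.6.1 defines it with two origins and one event: "TTP: defined as the time from 1) Day 0 ASCT and 2) Date of enrollment to progressive disease (PD) per IMWG criteria". Death is not an event. The same bullet then gives two censoring rules:

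- Alive without progression: "Subjects without documented PD or death will be censored at the last disease assessment date".
- Dead without progression: "subjects who died without documented PD will be censored at the time of death".

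Table 13 in 7.1.8.1 has a single TTP entry in its missing-data column: "Censored at the last non- PD assessment date". The analysis is descriptive, in the population of all enrolled subjects (7.1.7.1): "Kaplan-Meier estimates and corresponding 95% confidence intervals of time to event endpoints, including PFS, OS, TTP and DOR, will be provided".

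Section 6.1.2.11 sets when assessment stops: "Disease assessments should continue to be performed until documented disease progression, the start of new anti-cancer treatment", among other reasons. Section 6.1.4.5 sets off-treatment assessments 12 weeks apart (84 ± 7 days). After confirmed progression or new therapy, section 6.1.4.5.1 says "the subject moves into the survival follow-up phase and should be contacted by telephone every 12 weeks to assess for survival status". Section 7.0 states that no separate SAP will be issued, so no later document is planned that would settle the difference.

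**The concern.** The two rules agree for patients who are alive and differ for patients who die without documented progression. An analyst could follow either section and produce a different TTP curve.

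The 7.1.6.1 rule also has a structural fault. Take a patient last assessed at month 6 who then starts other therapy and dies at month 20. Under 7.1.6.1 this patient is at risk of progression until month 20, which adds 20 − 6 = 14 months in which no progression could be recorded. A patient with the same assessments who is alive at month 20 is censored at month 6. Time at risk then depends on a later event, which Kaplan-Meier estimation does not allow. Such therapy is foreseeable: treatment lasts four 21-day cycles, and section 4.5.2 prohibits no therapy in post-treatment follow-up.

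What is at stake is a secondary estimate that leans in the favourable direction, and a choice between two prespecified answers that could be made after the data are seen.

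**Working it through.** **Plan's own figures.** The documents give no figure for TTP. The Simon design for 12-month PFS (continue with at least 9 of 15, succeed with at least 27 of 43, p0 = 50%, p1 = 70%) does reproduce. Exact binomial calculation gives alpha 0.0499, power 0.804, probability of early termination 0.6964 and expected sample size 15 + (1 − 0.6964) × 28 = 23.50. TTP does not enter it.

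**Direction.** Let λ be the progression hazard. At time t, let N(t) be the fraction still assessed and progression-free, and W(t) the fraction no longer assessed whose later death keeps them in the risk set. With non-informative stopping, the hazard estimated under 7.1.6.1 is

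λ × N(t) / (N(t) + W(t)).

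Under Table 13, W(t) = 0. Since W(t) cannot be negative, the 7.1.6.1 curve is never below the Table 13 curve.

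**Length of the gap.** On the 12-week schedule alone it is at most 84 + 7 = 91 days, about 13 weeks. After new therapy it has no upper limit.

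**Size at 12 months.** Assumptions, none of them in the documents: exponential TTP; 5%, 10% or 20% of patients stop assessment at a uniform time between months 3 and 12 unless they progress first; they die 2.8, 6 or 9 months after stopping; stopping is unrelated to progression risk. The 14-month median is the centre's event-free survival figure in 3.2.1.2, used only as an illustration. It implies a true 12-month rate of 0.5^(12/14) = 55.2%. Simulating 400,000 patients per setting gives:

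| Share stopping | Table 13 rule | 7.1.6.1 rule |
|---|---|---|
| 5% | 55.1–55.3% | 55.5–56.0% |
| 10% | 55.2–55.3% | 55.9–56.7% |
| 20% | 55.1–55.3% | 56.8–58.0% |

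With a true rate of 70%, the 7.1.6.1 rule gives 70.2–72.0%. With 50%, it gives 50.4–53.1%. The bias runs from about 70.2 − 70.0 = 0.2 to 53.1 − 50.0 = 3.1 points.

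The formula can be checked at one point: 20% stopping, a 9-month gap, t = 12.

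- λ = ln 2 / 14 = 0.0495 per month.
- N = 0.8 × 0.552 = 0.4416.
- W = 0.2 × (e^(−3λ) − e^(−12λ)) / (9λ) = 0.1391.
- Ratio = 0.4416 / 0.5807 = 0.76.

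The estimated hazard is then 24% too low at month 12. Integrating the same expression from 0 to 12 months gives 58.1%, against 58.0% simulated.

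**Sampling error for comparison.** With 43 patients and a 55% rate, the 95% half-width is 1.96 × √(0.55 × 0.45 / 43) = 14.9 points before censoring.

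**Later times.** The Trial Summary plans 12 months of enrolment and about 24 months from first consent to last visit. Measured from enrolment, nobody is followed beyond 24 months. Measured from transplant, 60 to 180 days (about 2 to 6 months, mean 4) before entry, a patient enrolled in month u reaches month 24 only if u is no larger than that lag. Assuming uniform enrolment, that is 4/12, or about 14 of 43. The number also progression-free is at most 43 × 1/3 × 0.5^(24/14) = 4.4 with a 14-month median, or 43 × 1/3 × 0.7² = 7.0 if the 12-month rate is 70%. This is before patients are lost to new therapy or censored at an earlier assessment.

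A simulation on that calendar left 1 to 2 patients at risk at 24 months. It assumed 55% progression-free 8 months after entry, median death 10 or 18 months after progression, and a 0.003 monthly hazard of other death. The rules differed by 1.4–1.9 points at 24 months with 12% starting other therapy before progression, and by 4.6–6.6 points with 31%. At 12 months they differed by 0.6–2.1 points.

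**The case against.** The strongest reply is that this is a small consistency edit. TTP is untested and secondary, the 12-month difference is well inside sampling error, and the share of patients starting other therapy without documented progression appears nowhere in the documents. For everyone else the gap is about 13 weeks at most. All of that stands, and it limits the weight of the point.

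Sections 7.1 and 7.1.7.1 send the reader to 7.1.8 for full detail and missing-data handling, so Table 13 could be said to govern already. That supports the choice of rule, but it does not remove the contrary sentence. The opposite reading, that Table 13 is shorthand for the living-patient rule, is also possible, though the table does not say so.

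Section 3.2.3.1 dates progression at the start of the next line of therapy. If that applied to TTP, the month-6 to month-20 patient would have an event when therapy began and the mechanism would largely vanish. But that text concerns PFS and itself differs from 7.1.6.1.

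A reader might infer that TTP at 24 months is overstated by around ten points. Gaps of that size need 36 months of follow-up and about a third of patients starting other therapy first. The Trial Summary plans about 24 months, and no section gives such a rate. The timeline is approximate, however, and the 12-month interim look could lengthen it.

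**Conclusion.** The contradiction between 7.1.6.1 and Table 13 is certain from the text. So is the ordering: death-date censoring can only raise the TTP curve or leave it unchanged. The upward bias at 12 months is about 0.2 to 3 percentage points, given 5% to 20% stopping assessment before progression, death 2.8 to 9 months later, and stopping unrelated to progression risk. It may be larger later, where few patients remain at risk.

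Two further inferences are not supported. One is that the primary result is affected: PFS counts death as an event, so its decision rule, the 43 patients and the power stand. The other is that Table 13 gives an unbiased answer: if new therapy is started for suspected progression, neither rule is unbiased. It is worth correcting because the change is cheap and removes a choice between two prespecified answers.

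**What to change.** In 7.1.6.1, replace the TTP censoring text with one rule: all subjects without documented progression, including those who died, are censored at the last disease assessment without progression. State that it applies to both origins (day 0 of transplant and date of enrolment), so that it matches Table 13. Keep death-date censoring as a named sensitivity analysis.

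The cost is one sentence and one extra run of the curve, with no new data, visits or patients. The TTP estimate becomes slightly less favourable. The change does not cure informative stopping, so the report should also give the number of patients who started other therapy before documented progression and the number of those who died.

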### **7.1.6.2 Safety Endpoints**

The primary safety endpoints include the AEs graded using CTCAE (Version 4.03) criteria. Safety will be assessed by quantifying the toxicities and grades experienced by subjects who have received pembrolizumab (MK-3475), including serious AEs and events of clinical interest (ECIs). Immune-related AEs (irAEs), as defined in Section 6.2.3.2 will be collected. Other safety endpoints include laboratory safety assessments, vital signs and physical examinations. Safety measurements are described in Section 6.

### **7.1.7 Analysis Populations**

#### **7.1.7.1 Efficacy Analysis Populations**

The Full Analysis Set (FAS) population will serve as the primary population for the analysis of response rate data in this study. The FAS population consists of all subjects who:

- receive at least one dose of study treatment
- have a post baseline disease assessment OR discontinue the trial due to progressive disease/drug-related AE

The Intent-to-Treat (ITT) population will serve as the primary population for the analyses of PFS, TTP and OS in this study. The ITT population consists of all enrolled subjects.

The analysis of response duration is based on all responders.

Details on the approach to handling missing data are provided in Section 7.1.8 Statistical Methods.

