#### **7.1.1 Efficacy Analysis**

The primary and key secondary endpoints, primary analysis population, and statistical methods that will be employed for the efficacy analysis are presented in Table 11 below.

The CR+sCR+VGPR response rate and objective response rate (ORR) per IMWG criteria based on investigator assessment will be conducted in the Full Analysis Set (FAS) population. No multiplicity adjustment is planned.

Table 12: Summary of Analysis Strategy for Key Efficacy Endpoints

Endpoint/Variable (Description, Time point)	Statistical Method	Analysis Population	Missing Data Approach
PFS	Kaplan Meier	FAS	Subjects with missing data are considered non-progressors
CR + sCR + VGPR response rate per IMWG criteria based on	Exact test of binomial parameter	FAS	Subjects with missing data are considered non-responders

investigator assessment			
ORR per IMWG criteria based on investigator assessment	Exact test of binomial parameter	FAS	Subjects with missing data are considered non-responders

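### The primary response-rate population leaves out dosed subjects with no post-baseline assessment who left for reasons other than progression or a drug-related AE, so missing = non-responder cannot reach them

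*Combined protocol and SAP*

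**What the plan says.** Section 7.1.7.1 states: "The Full Analysis Set (FAS) population will serve as the primary population for the analysis of response rate data in this study". Membership has two conditions. The subject must "receive at least one dose of study treatment" and must also "have a post baseline disease assessment OR discontinue the trial due to progressive disease/drug-related AE". The same section defines the alternative population: "The ITT population consists of all enrolled subjects".

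The missing-data rule appears in three places. The ORR definition in section 7.1.6.1 reads "Subjects with missing outcome on objective response will be considered non-responders". Table 13 in section 7.1.8.1 reads "Subjects with missing data are considered as non-responders" for both ORR and CR+sCR+VGPR, with FAS as the primary and ITT as the supportive population. Table 12 repeats the rule but lists FAS only, and the text of section 7.1.1 says that the response analyses "will be conducted in the Full Analysis Set (FAS) population".

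Section 7.1.8.1 attaches inference to these rates: "the point estimate, 90% confidence interval and p-value for testing response rate is greater than the historical control for each arm", by the exact binomial distribution. No historical response rate is given. Section 7.1.8.3 says that reasons for exclusion from FAS will be summarised.

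**The concern.** A missing = non-responder rule protects a single-arm response rate against losing its failures. It works only for subjects who are still in the denominator. The second FAS condition removes some of the subjects the rule is meant for: those dosed, never reassessed, and gone for a reason other than progression or a drug-related AE. Section 4.8 lists such reasons, among them withdrawn consent, intercurrent illness, investigator decision, noncompliance and loss to follow-up.

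Membership also depends partly on a judgment made after treatment has started. The trial is open label, and the investigator assesses both response and AE causality. Table 11 in section 6.2.4 rates causality against the Merck product only, and section 7.1.7.1 does not define what drug-related means. A subject who stops before reassessment because of an AE attributed to lenalidomide or dexamethasone could be placed inside or outside FAS.

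At stake are the headline response rates, their 90% intervals and the p-values against a historical control.

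**Working it through.** **Plan's own figures.** The plan gives no sample size, power or expected rate for response. Its N of 43 comes from the Simon design for 12-month PFS (sections 7.1.3 and 7.1.10). Exact binomial enumeration with boundaries 8/15 and 26/43, p0 = 50% and p1 = 70% gives early termination 0.6964, expected N 23.50, one-sided alpha 0.0499 and power 0.804. These agree with the stated 0.696, 23.5, 0.05 and 80%. The design stands, and response plays no part in it.

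**Who is excluded.** Take dosed subjects and cross assessment status with reason for leaving:

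| Dosed subject | In FAS? | Does missing = non-responder apply? |
|---|---|---|
| At least one post-baseline assessment, any reason for leaving | Yes | Yes, if response cannot be determined |
| No assessment, left for progression or drug-related AE | Yes | Yes |
| No assessment, left for another reason | No | No |

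Only the last row is affected.

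**Direction.** Appendix 11.5 requires two consecutive assessments for every response category. On the Cycle 1 day 1/screening baseline, a subject in the last row therefore cannot be a responder. Exclusion shrinks the denominator and leaves the numerator alone.

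**Size.** Let x be responders, N all dosed subjects and k those excluded.

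FAS rate = x/(N−k) = (x/N) × N/(N−k)

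The documents give neither x nor k. Assume N = 43 (the plan calls these evaluable, so the number dosed could differ) and x = 26, for illustration. Intervals are exact 90% Clopper-Pearson.

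| k (assumed) | FAS rate | 90% CI | Gain over 26/43 |
|---|---|---|---|
| 0 | 26/43 = 60.5% | 46.8–73.0 | 0 |
| 1 | 26/42 = 61.9% | 48.0–74.4 | 1.4 points |
| 2 | 26/41 = 63.4% | 49.4–75.9 | 2.9 points |
| 4 | 26/39 = 66.7% | 52.3–79.0 | 6.2 points |
| 6 | 26/37 = 70.3% | 55.6–82.3 | 9.8 points |

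Across 22 to 34 responders of 43, the gain is 1.2 to 1.9 points at k = 1, 2.5 to 3.9 at k = 2, 5.2 to 8.1 at k = 4 and 8.3 to 12.8 at k = 6.

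**Effect on the test.** Assume a historical response rate of 50% and a one-sided exact test at 0.05 (the plan states neither for response). Let the true rate among all 43 equal 50%, with the k excluded subjects all non-responders. The test uses n = 43−k and the smallest critical value r with P(X ≥ r | n, 0.5) ≤ 0.05. Its actual size is P(X ≥ r | n, 0.5 × 43/n):

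- k = 0: n = 43, r = 28, size 0.033
- k = 1: n = 42, r = 27, size 0.061
- k = 2: n = 41, r = 27, size 0.058
- k = 4: n = 39, r = 26, size 0.098

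The small dip from k = 1 to k = 2 comes from the discreteness of the exact test.

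**The case against.** The strongest reply is that few subjects, perhaps none, will fall into the excluded group. Leaving early is not enough, because one post-baseline assessment keeps a subject in FAS. Response is assessed every 21-day cycle (section 6.1.2.9), with the first on-treatment reassessment at Cycle 2 day 1. Final-visit procedures are due at discontinuation (section 6.1.4.1). Flow chart note 18 asks for a response assessment when treatment stops without confirmed progression, and section 6.1.4.5 continues disease follow-up every 12 weeks. This stands. What remains is mainly very early deaths, withdrawals of consent and losses to follow-up, where a final visit cannot be relied on.

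The choice of baseline also matters. Section 7.1.6.1 computes response from two baselines: before ASCT, and Cycle 1 day 1 or screening. Section 7.1.7.1 does not say which one the FAS condition refers to. If it is the pre-ASCT baseline, the screening assessment already qualifies and k is close to zero. This stands too, and it is itself a gap in the definition.

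A reader might infer that the FAS definition cancels the non-responder rule altogether. The documents do not support that. Within FAS the rule still covers subjects who left for progression or a drug-related AE without an assessment, and those assessed without a determinable response. It also applies in full to the supportive ITT analysis in Table 13. With that analysis and the summary of FAS exclusions, a reader of the results could see both denominators.

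**Conclusion.** The point holds in a narrow form. For dosed subjects with no post-baseline assessment who left for reasons other than progression or a drug-related AE, the primary response analysis drops what the plan's own rule would count as failures. Any bias is upward, by the factor N/(N−k). In the illustration it is 2.9 points at two exclusions and 6.2 at four, and it vanishes at none. The size rests on assumed values of x, k and N, and the test-size figures also on an assumed control rate of 50%. The upward direction is most secure for the study-drug baseline.

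A reader might also infer that response rates will be materially inflated, or that the trial's efficacy conclusion is at risk. Neither follows. The number excluded is unknown and probably small. Response is secondary with no success threshold, and the interim rule and final decision rest on 12-month PFS. This is a cheap improvement.

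**What to change.** For ORR and CR+sCR+VGPR, delete the second FAS condition in section 7.1.7.1. The primary denominator becomes all subjects who received at least one dose, with missing = non-responder. This removes the dependence on the reason for leaving and on which baseline is meant, and it matches the existing definition of the as-treated safety population. Keep ITT as supportive.

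Alternatively, make the already planned ITT analysis primary in Table 13 and keep FAS as supportive. In that case state in section 7.1.7.1 which baseline the post-baseline condition uses.

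Either way, make the response rows of Table 12, the text of section 7.1.1, section 7.1.7.1 and Table 13 agree. Section 7.0 says no separate SAP will be issued, so the change belongs in the protocol text.

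The cost is a wording change, with no new data and no change to the sample size. The headline rate may be slightly lower. If ITT is chosen, enrolled subjects who were never dosed count as non-responders, which the all-dosed denominator avoids.
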